### Primary Study Objective:

The primary endpoint of this Phase IIb feasibility trial will be the demonstration of the prevention of seizures and the subsequent cognitive assessment component of the Bayley-III. The other components of the Bayley (receptive communication, expressive communication, fine and gross motor subscores) will be used as secondary and supportive endpoints. The primary goal of this Phase IIb trial will be to provide the evidence needed for a Phase III pivotal trial. Thus, the study will need to demonstrate the purported mechanism by which an improved clinical outcome is achieved, prevention of seizures, leading to a difference in cognitive outcomes. The rationale for not using a composite outcome at this stage of evaluation is that it will be simpler to focus on a single most promising outcome measure of early treatment and one that is clinically meaningful. The other components of the Bayley-III will be evaluated in a multivariate composite as part of the secondary outcomes and exploratory outcome.

The sample size for this feasibility trial is derived from the resources available to support the trial as per this NINDS mechanism, the primary goal of demonstrating a reduction in seizures and the power to assess the differences in cognitive scores on the Bayley-III. To assess the plausibility of recruitment, we looked at the pilot data from our ongoing TSC

Project. To date, we have enrolled 40 patients, 1 patient dropped out; 15 continue without seizures to date; 19 developed well controlled seizures, and 5 have developed refractory seizures. Thus, 25 of the 40 or almost two thirds of the enrolled patients have developed seizures to date. Reducing this number with earlier intervention would seem consistent with achieving a positive effect on the cognitive outcomes as assessed by the Bayley-III.

[figure not shown]
[figure not shown]
[figure not shown]
[figure not shown]
We expect to be able to recruit between 75 and 80 participants over the course of the recruitment period. Based on these numbers we expect 37.5% (based on our P20 data where 15/40 remained seizure free) to be biomarker free and never randomized. Thus, we expect to lose to randomization between 28 to 30 participants yielding approximately 48 patients to be randomized ( $75-28 = 47$  and  $80-30=50$ ) or 24 to 25 participants per group.

To estimate sample size needed, we first assess the ability to demonstrate the feasibility that the intervening variable, seizures, can be prevented with early treatment. In the placebo arm, we expect that all patients will develop seizures, but to be conservative we assume that 2/24 in the placebo arm do not develop a seizure within the time frame, making the proportion of seizure occurrence 0.917. In the vigabatrin arm, we assume it mirrors the proportion well controlled in our ongoing TSC project, thus our seizure rate will be estimated at 5/24 (19 remain seizure free to date) or 0.208. A Fisher's exact test with a 0.05 two-sided significance level will have 99% power to detect the difference between a Group 1 proportion,  $p_1$ , of 0.917 and a Group 2 proportion,  $p_2$ , of 0.208 when the sample size in each group is 24.

The percent difference for seizures used in the power calculation is based on data collected during our current TSC project. We note that this is a large difference. However, it is conservatively estimated through discounting our expected 100% seizure rate in the control arm to 91.7% and using our observed data for the treatment arm, which under a strict protocol could be higher. Even if the vigabatrin treatment is less effective than expected and 10/24 (0.417) in the treatment arm experience seizures, we still have greater than 90% power to detect this treatment effect.

We proposed the percent difference in cognitive scores also based on our ongoing work. We have found that the distribution of Mullen Scales of early development show that by two years there is a substantial downward shift in scores (bottom right figure (red graph) below for the 24 month results). The mean at 6 months was 89.9 (sd=18.1) and mean at 24 months 75.7 (sd=22.1). The estimated standard deviation of the change is 4 points (assuming a correlation of 0.60 between the two time points as is consistent with the correlations of Bayley's over time). With the mean decline of over 14 points from 6 months to 24 months on average, with a standard deviation of 4 points, there is a great deal of potential for an intervention to achieve an effect size of 0.889 (our proposed effect size based on differences amongst disease groups on the Bayley's). This effect size would be approximately 3.5 points on the Mullen Scale. This would amount to a percent reduction in the decline of  $3.5/14.2$  or about 25% of the natural decline, which seems reasonable for a drug intervention. Thus, our pilot data once again provide reasonable evidence that our intervention effects are achievable.

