- (5) Preliminary results of video EEG biomarker analysis from the NIH P20 grant-*Potential EEG Biomarkers and Antiepileptogenic Strategies for Epilepsy in TSC* (P20-NS080199) are compelling and support the use of the presence of epileptiform activity as an EEG biomarker for the PREVeNT Trial. The conventional EEG data analysis was focused on infants 6 to 24 months of age, when clinical seizures were more likely to emerge in the TSC population. The presence of inter-ictal EEG epileptiform activity and developing seizures had a sensitivity of 73.7% and specificity of 100%. The corresponding positive predictive value (PPV) for inter-ictal EEG epileptiform activity is 100% (that the subject with epileptiform discharges on EEG would develop seizures) and negative predictive value (NPV) is 64% (that the subject without epileptiform discharges on EEG would not develop seizures).

The central hypothesis of this Phase IIb trial is that early identification of electroencephalography (EEG) biomarkers and early treatment versus delayed treatment with vigabatrin in infants with TSC will have a positive impact on developmental outcomes at 24 months of age. It would also prevent or lower the risk of developing infantile spasms and refractory seizures. This preventative approach would be expected to result in more favorable long-term cognitive, behavioral, developmental and psychiatric outcomes and significantly improve overall quality of life. It is a randomized, double-blind, placebo-controlled clinical trial design. Successful completion of this trial will also advance the field by demonstrating the value of systematic surveillance with EEG in asymptomatic infants with TSC.

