If an enrolled subject has an electrographic or clinical seizure(s) prior to randomization and the previous EEG(s) have been normal they will move into the Open label phase of the study (Arm B). If the seizures are not controlled in the Open label phase at the vigabatrin maximum dose of 150mg/kg/day, the investigator may change the antiepileptic medication as clinically warranted to improve seizure control (including tapering off vigabatrin). These subjects will remain in the open arm of the study for the duration of the protocol (36 months).

Patients enrolled without prior clinical seizures but found on first baseline EEG to have electrographic or clinical seizures of which the parent and clinician were previously unaware will exit the PREVeNT trial and begin medical treatment by the site PI based on clinically accepted management guidelines for seizures in TSC infants. Based on the P20-NS080199 study, this group is estimated to be very small (<5%) and will not affect the total number of enrolled patients (N=80) eligible to be randomized to either placebo or vigabatrin treatment.

Enrolled subjects who never develop EEG abnormalities or clinical seizures (ARM C) will remain in the study and continue with regular clinical evaluations, EEG testing, and developmental assessments as scheduled (Table 2). Without EEG change or developing seizures, they will have neither been randomized nor treated with vigabatrin. These patients will serve as a negative control and be key for validating the sensitivity and specificity of EEG biomarkers as predictors of seizure risk and baseline disease characteristics attributable to TSC that are independent of epilepsy and AED treatment (TREATMENT ARM A).

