If electrographic or clinical seizures occur while on study drug, they will transition into the Open label phase of the study (Arm B) and continue to be followed until 36 months of age as per the PREVeNT protocol schedule. If the seizures are not controlled in the Open label phase at the vigabatrin maximum dose of 150mg/kg/day, the investigator may change the antiepileptic medication as clinically warranted to improve seizure control (including tapering off vigabatrin). These subjects will remain in the open arm of the study for the duration of the protocol (36 months).

Based on the TSC-EBS data, it is estimated that 30% of subjects (24 subjects) in Arm C will not be treated but continue in the study until the age of 36 months (Table 2).

See Pharmacy Manual for details of packaging and labeling, product tracking and accountability, and product disposal and destruction.

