## Early Global Development in Tuberous Sclerosis

In addition, for the cognitive outcomes, using a t-test on the final Bayley-III Cognitive Scores shows that when the sample size is 24 participants per arm there is 85% power to detect an effect size on the cognitive component of the Bayley III of 0.885 when the Type I error is 0.05, two tailed. The plausibility of achieving this effect size was assessed using published data from the Bayley III manual. In children with Pervasive Developmental Disorders, the average cognitive score is 5.7 (sd 2.9) compared to matched controls with a mean of 11.0 (sd 3.0). The effect size for the difference between this disorder and the matched controls is 1.77  $[(11.0-5.7)/3.0]$ , a difference double the effect size detectable with the sample size available for this Phase IIb trial. While it is unlikely that early treatment would return these patients to normal levels, we are hypothesizing as the alternative that we will achieve an effect size of approximately 50% of the difference compared to normal scores. That is, we will use a sample size necessary to detect an effect size of 0.885.

To further examine the ability of the sample size to achieve the goals of the study, we first examined the sensitivity of the design to our assumption of the standard deviation by examining the standard deviation against other groups of special interest.

The Bayley-III cognitive test battery shows that the standard deviations vary from a low of 1.9 at an assessment in Downs Syndrome Children to 3.5 amongst SGA infants. The table below shows the standard deviations for various special groups.

PDD	CP	DD	Language impaired	Perf At Risk	Asphyx	Fetal Alcohol	SGA	Premie
2.9	3.1	1.9	2.4	3.2	3.1	2.7	3.5	3.1

The average standard deviation is 2.9, the median is 3.1, so again, using 3.0 in our calculations seemed reasonable.

We next estimated the sensitivity of the trial in terms of the power for testing the time-averaged difference (TAD) between two means in a *repeated measures* design. In the TAD model, we assumed the mean difference starts to become evident at 3 months and is continuing or enlarging at 12, 24 and 36 months. The correlation amongst Bayley-III Cognitive assessments within person was varied from 0.10 to 0.80.

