EEG biomarker feasibility: The outcome measure will be the sensitivity and specificity of EEG epileptiform activity in predicting outcomes at 24 months for each treatment group. To confirm the feasibility of using EEG biomarkers to identify TSC infants at risk for developing epilepsy, sensitivity and specificity of EEG epileptiform activity at each time-point for predicting subsequent development of epilepsy by 24 months of age will be conducted within each treatment arm. Successful treatment in the vigabatrin arm should produce significantly poorer specificity and lower positive predictive value (PPV) by mitigating the predictive power of the EEG epileptiform activity. Exploratory analysis will further evaluate the timing of EEG change with time to seizure onset and type of EEG change with epilepsy type and treatment response as a covariate in the Cox proportional hazards assessment of time to clinical seizure. Additional analysis will evaluate the separate impact of TSC clinical features and concurrent AEDs. Our estimate is that 75% will develop the EEG biomarker prior to clinical seizures, some of the enrolled infants will

develop neither EEG biomarker nor seizures and some will develop seizures prior to being identified with the EEG biomarker or never develop the EEG biomarker despite the onset of clinical seizures. If the incidence of developing the EEG biomarker relative to the incidence of seizures without the EEG biomarker is very low, then the efficacy of treatment would have to be great to warrant the cost of monitoring. Thus, evaluation of this aim will be a tradeoff between biomarker incidences versus the treatment benefit. Descriptive statistics and numbers needed to treat (NNT) will be used to evaluate this endpoint.

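### The 47 to 50 randomised, and hence the 85% power, do not follow from the plan's own inputs, because children who seize before an epileptiform EEG are counted as randomised

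*Combined protocol and SAP*

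**What the plan says.** The Primary Study Objective part of the statistical section states: "We expect to be able to recruit between 75 and 80 participants over the course of the recruitment period". It takes the pilot's 15 of 40 seizure-free children as the share expected "to be biomarker free and never randomized. Thus, we expect to lose to randomization between 28 to 30 participants". Subtraction leaves about 48 randomised (47 to 50), or 24 to 25 per group. Monitoring Recruitment uses the complement, 62.5%, as the biomarker-positive share. For the Bayley-III cognitive score with 24 per arm, "there is 85% power to detect an effect size" of 0.885 at two-sided 0.05.

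Other sections bear on this flow:

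- The design text after the exclusion criteria: "If an enrolled subject has an electrographic or clinical seizure(s) prior to randomization and the previous EEG(s) have been normal they will move" to the open-label phase (Arm B). They are not randomised.
- EEG biomarker feasibility accepts that "some will develop seizures prior to being identified with the EEG biomarker". It also estimates that 75% will show the biomarker before clinical seizures, without giving a denominator.
- The Background reports, for the pilot EEG, a "sensitivity of 73.7% and specificity of 100" per cent, with a negative predictive value of 64%.
- Vigabatrin and Placebo: "it is estimated that 30% of subjects (24 subjects) in Arm C will not be treated". The safety text under Additional developmental measures and ASD Risk puts the negative controls at 15 to 20.
- Additional measures and analyses considerations gives 28 to 30 not randomised, and there includes children with electrographic seizures at baseline. The design text says those children exit the study.
- The pilot summary says "25 of the 40 or almost two thirds of the enrolled patients have developed seizures to date".

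**The concern.** Seizure free and biomarker free are different states. The flow treats them as one, so every child expected to seize is assumed to show an epileptiform EEG first and be randomised. The protocol provides a separate route for children who do not, says that some will occur, and reports a sensitivity implying that about 26% of pilot seizure cases had no epileptiform EEG (100% − 73.7% = 26.3%). The sample-size text allots them no one.

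Twenty-four per arm is the sole basis for the 85% power on the Bayley-III outcome, which informs the Phase III decision. If the arms are smaller, a null result could be read as if the trial had been adequately powered for an effect of 0.885.

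**Working it through.** **1. The plan's figures.** Randomised: 0.625 × 75 = 46.9 and 0.625 × 80 = 50.0, matching 47 to 50. Power of a two-sided two-sample t-test (noncentral t, alpha 0.05, d = 0.885, 24 per arm): 85.1%. Both reproduce. The arithmetic is sound, and the fault is in the flow that feeds it.

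**2. The flow with the missing term.** Let N be the number enrolled, s the share who seize, and b the share of those with an epileptiform EEG before the seizure. If no seizure-free child becomes biomarker positive (the pilot's 100% specificity), randomised = N × s × b, split 1:1. The plan implicitly sets b = 1.

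**3. Number randomised and power at d = 0.885, using figures in the plan.**

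| Inputs | Randomised | Power |
|---|---|---|
| Seizing 62.5%, sensitivity 73.7%: 75 or 80 × 0.625 × 0.737 | 34.5 to 36.9 | 71 to 74% |
| Seizing 62.5%, with the 75% read as a share of seizure cases: 75 or 80 × 0.625 × 0.75 | 35.2 to 37.5 | 72 to 75% |
| Arm C 30%, the rest × 73.7%: 75 or 80 × 0.70 × 0.737 | 38.7 to 41.3 | 76 to 79% |
| Arm C 20 or 15 of 80, the rest × 73.7%: 60 or 65 × 0.737 | 44.2 to 47.9 | 82 to 85% |
| 75% read as a share of all enrolled: 75 or 80 × 0.75 | 56 to 60 | 90 to 92% |

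**4. Cross-check from the pilot's predictive values.** With sensitivity 0.737, specificity 1 and negative predictive value 0.64, the share seizing in that analysis is 0.36 / (0.36 + 0.64 × 0.263) = 0.68. The biomarker-positive share is then 0.68 × 0.737 = 0.50, not 0.625. At 50%, 75 to 80 enrolled give 37.5 to 40 randomised and 75 to 78% power.

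**5. Detectable effect.** For 85% power, d must be 1.06 at 17 per arm and 1.03 at 18 per arm.

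**6. Seizure comparison (exact Fisher power).** For 0.917 against 0.208, power is 99.4 to 99.7% at 17 to 18 per arm, so the main claim survives. For the fallback, 0.917 against 0.417, it is 96% at 24 per arm, 92% at 20, and 84 to 87% at 17 to 18. The stated value is above 90%.

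**7. Pilot count.** 1 dropout + 15 + 19 + 5 = 40, so 19 + 5 = 24 children seized. The 25 includes the dropout. The effect is small: 24/40 gives 45 to 48 and 24/39 gives 46 to 49 by the plan's own method.

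**8. The recruitment check.** At 80 screened the table's lower limit is 36.1. An expected 36.9 lies above it. At 30 screened the limit is 10.3, against an expected 30 × 0.461 = 13.8.

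**The case against.** A reader might infer that the trial will randomise only about 35 to 41 children and that the 85% power will not be delivered. The documents do not support that, for four reasons.

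- The 75% in EEG biomarker feasibility is followed by a description of the remaining enrolled infants, so it can be read as a share of all enrolled. That gives 56 to 60 randomised and fits 15 to 20 negative controls (60 + 15 to 20 = 75 to 80). It does not fit the 24 in Arm C or the 62.5%.
- Carrying 73.7% over is an assumption. It comes from an analysis centred on ages 6 to 24 months, while trial EEGs can start at about 6 weeks of age. The Background does not say whether the EEG change came before the seizure. If specificity is below 100%, some seizure-free children would also be randomised.
- Pilot seizure status was to date. The Background's 80 to 90% lifetime rate, taken as an upper case, gives 75 × 0.80 × 0.737 = 44 to 80 × 0.90 × 0.737 = 53 randomised, or 82 to 89% power.
- Enrolment can be reviewed. Monitoring Recruitment plans an EEG analysis once 28 subjects reach 12 months, and names adding sites or extending recruitment.

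All four stand as limits on the size of the problem. None repairs the flow. The favourable readings contradict its own 28 to 30 never randomised, and no section supports b = 1. The review is only a partial safeguard, since its table uses the same 62.5% and its limits are loose.

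The plan also expects repeated measures to lift power slightly above 85%, but the gain is not quantified and starts from the same 24 per arm. The feasibility setting and resource-based sample size lower the severity, not the need for correct figures.

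**Conclusion.** Wrong as written; should be fixed. The 47 to 50 randomised and the 85% power are unsupported, because the flow equates seizure free with biomarker free and omits the seizure-first route to Arm B. The plan's own figures span about 35 to 60 randomised and 71 to 92% power. The values below 85% rest on the 73.7% carry-over or on reading the 75% as a share of seizure cases. The values of 90% or more require that 75% to mean all enrolled. The range includes 85%, so the conclusion is that the stated power is not justified, not that it is known to be missed.

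The main seizure comparison is little affected, but its fallback claim of more than 90% power fails at 17 to 18 per arm. The miscounted dropout is minor. Of the differing group sizes, 24 against 15 to 20 is the like-for-like conflict. The 28 to 30 in Additional measures and analyses considerations describes a wider group.

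**What to change.** 1. Replace the flow with one split of the 75 to 80 enrolled into Arm A (randomised), direct Arm B (seizure first), Arm C and baseline exits. Use it in Vigabatrin and Placebo, Monitoring Recruitment, Primary Study Objective, Additional developmental measures and ASD Risk, EEG biomarker feasibility, and Additional measures and analyses considerations. The passages on children with seizures at baseline must be reconciled.
2. State the denominator of the 75%.
3. Correct 25/40 to 24/40 (or 24/39).
4. Give the number randomised and the t-test power at d = 0.885 as a range, each value with its assumption: the first, third, fourth and fifth rows of the table above. Add the detectable effect of about 1.03 to 1.06 SD at 17 to 18 per arm.
5. Restate the fallback power for the seizure comparison as 84 to 87% at 17 to 18 per arm.
6. Note that the interim recruitment check rests on the same 62.5% and revise its expected share to match the new split.

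Cost: protocol wording only. The stated power may become less favourable. No additional enrolment is required.

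### The 0.208 vigabatrin-arm seizure rate is a refractory share among pilot children who had already had seizures, so the pilot data do not support it as a first-seizure rate

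*Combined protocol and SAP*

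**What the plan says.** All of this is in the Combined protocol and SAP, under Primary Study Objective in the statistical section.

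- **Pilot counts.** The plan opens with "To date, we have enrolled 40 patients, 1 patient dropped out; 15 continue without seizures to date". It then describes the remaining children, all of whom had seizures: "19 developed well controlled seizures, and 5 have developed refractory seizures".
- **Placebo-arm rate.** The plan expects every placebo child to have a seizure but discounts this: "we assume that 2/24 in the placebo arm do not develop a seizure within the time frame, making the proportion of seizure occurrence 0.917".
- **Vigabatrin-arm rate.** "In the vigabatrin arm, we assume it mirrors the proportion well controlled in our ongoing TSC project", and "thus our seizure rate will be estimated at 5/24 (19 remain seizure free to date) or 0.208".
- **Power.** "A Fisher's exact test with a 0.05 two-sided significance level will have 99% power to detect the difference" between those two proportions, "when the sample size in each group is 24".
- **Justification.** The plan accepts that the difference is large but calls it conservative on two grounds: the placebo discount, and "using our observed data for the treatment arm, which under a strict protocol could be higher".
- **Fallback.** It adds that power still exceeds 90% if 10/24 (0.417) of the vigabatrin arm have seizures. No source is given for 10/24.

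The endpoint is a first seizure. Secondary Study Objectives uses time to first clinical seizure after randomization. Analyses compares the proportions seizure free at two years with a chi-square test, by intention to treat.

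**The concern.** The same 19 children are described in two incompatible ways. In the pilot summary they developed seizures; in the power paragraph they are seizure free. On a first-seizure endpoint, a child whose seizures begin and are later controlled is an event, so the 19 cannot count as successes.

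The statistical section makes seizure prevention part of the primary endpoint, one of the reasons for the sample size, and the first analysis step, ahead of the Bayley-III comparison that informs the Phase III decision. A reader would take it that pilot data from comparable children support 99% power for that step. They do not, and power depends strongly on this rate.

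**Working it through.** **1. Pilot counts.** 1 dropout + 15 without seizures + 19 controlled + 5 refractory = 40. The denominator of 5/24 is 19 + 5 = 24, which are exactly the children who had seizures. It coincides with the planned 24 per arm but is a different quantity. The 15 seizure-free children do not enter it. (The section's count of 25 of 40 with seizures appears to include the dropout. That figure is not used in this power calculation.)

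**2. What 5/24 measures.** 5/24 = 0.208 is the proportion refractory among children with seizures. On the trial's endpoint the same 24 children contribute 24 events. That does not make 24/24 the right vigabatrin rate either: the group is defined by having had seizures, so its rate is 100% by construction. The pilot counts as reported give no first-seizure rate under preventive vigabatrin.

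**3. The plan's power reproduced.** Inputs: n = 24 per arm, two-sided 0.05, p1 = 0.917, p2 = 0.208. Exact power is the sum, over all 25 × 25 outcomes (x, y) for which the test gives p ≤ 0.05, of Bin(x; 24, p1) × Bin(y; 24, p2).

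- 0.917 versus 0.208: Fisher 99.98% (stated 99%).
- 0.917 versus 0.417: Fisher 96.3% (stated above 90%).

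Both statements hold on their inputs.

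**4. Power over a range of vigabatrin rates.** Placebo rate 0.917, 24 per arm, same formula. The second column replaces Fisher's test with the Pearson chi-square without continuity correction. The plan names a chi-square test but does not mention a correction.

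| Vigabatrin rate | Fisher | Chi-square |
|---|---|---|
| 0.208 | >99.9% | >99.9% |
| 0.30 | >99% | >99% |
| 0.417 | 96% | 98% |
| 0.50 | 88% | 93% |
| 0.55 | 79% | 87% |
| 0.60 | 68% | 78% |
| 0.70 | 39% | 51% |

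**5. Detectable rates.** Solving for the vigabatrin rate at a given power:

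- Fisher: 90% at about 0.485, 80% at about 0.545.
- Uncorrected chi-square: 90% at about 0.53, 80% at about 0.59.

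Fisher power falls below 99% once the vigabatrin rate passes about 0.35.

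**The case against.** Several points on the other side are sound.

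- **The arithmetic is correct.** Both power statements reproduce. A reader might infer a calculation error; there is none.
- **The plan is partly open about the assumption.** It says that it assumes the rate, admits that the difference is large, and shows power at twice the rate. The 10/24 case does not use the 19 children, although it has no source either. Analyses says that a preventive effect is untested.
- **One ground for calling the difference conservative survives.** Discounting the placebo rate from 100% to 91.7% does not depend on 5/24. Only the ground that cites observed treatment-arm data fails.
- **The seizure comparison is not the only driver of the sample size.** The section also cites available resources and the Bayley-III calculation, which has 85% power and is the tighter of the two. Study Objectives names the Bayley-III cognitive score as the primary outcome and lists seizures as secondary. The statistical section gives seizures more weight.

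A reader might also infer that the trial is underpowered for seizures. The documents do not show that: with placebo at 0.917, power stays at 80% or more up to a vigabatrin rate of about 0.545 (Fisher) or 0.59 (chi-square).

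A lower placebo rate would change the picture, but that is a separate question. The biomarker figures in the background section (sensitivity 73.7%, positive predictive value 100%, negative predictive value 64%) fit 14 of 14 positives developing seizures, since 14/19 = 73.7% and 9/14 = 64%. The exact lower 95% limit for 14/14 is 0.025^(1/14) = 0.77. With placebo at 0.77, Fisher power at 0.417 is 63%. However, those counts are back-calculated, and 0.77 is a confidence limit of an observed 100%, not an estimate. It serves as a sensitivity case only.

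Reading seizure free as free of seizures on treatment at present does not rescue 5/24, because those children had already had a first seizure.

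**Conclusion.** The concern holds as a fault in the source of one input. The rate of 0.208 comes from relabelling 19 children with controlled seizures as seizure free. It measures a different outcome from the trial's, so the 99% cannot be presented as resting on observed treatment-arm data. How far true power differs is unknown, because the documents give no first-seizure rate under preventive vigabatrin. At a placebo rate of 0.917, Fisher power runs from over 99.9% at 0.208 to 39% at 0.70.

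These figures assume exact binomial power, 24 analysed per arm with no loss, and a chi-square test without continuity correction. They do not show that the design is inadequate or that the sample size should change.

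**What to change.** In the power paragraphs under Primary Study Objective:

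1. Delete the 5/24 derivation, the description of the 19 children as seizure free, and the statement that the treatment-arm rate uses observed data.
2. Limit the claim of conservatism to the placebo discount.
3. Label the vigabatrin rate an assumption, and do the same for 10/24 unless a source is given.
4. State the detectable difference for 24 per arm with placebo at 0.917, and name the test: 90% power at about 0.485 and 80% at about 0.545 for Fisher; about 0.53 and 0.59 for the uncorrected chi-square. The power statement should use the test that Analyses plans, or say why it differs.
5. Show power over vigabatrin rates from 0.2 to 0.7. Mark any lower placebo rate, such as 0.77, as an assumed sensitivity case.

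This is a change of wording plus a small table. Sample size, endpoints and analyses stay as they are. The only cost is a less favourable power statement.

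### The SD of change of 4 Mullen points does not follow from the plan's own SDs and correlation, which give 18.3; the 3.5-point and 25%-of-decline figures built on it are wrong

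*Combined protocol and SAP*

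**What the plan says.** The paragraph is in the combined protocol and SAP, under Statistical Methods, Sample Size and Analysis Plan, Primary Study Objective, just before the heading Early Global Development in Tuberous Sclerosis. It reports pilot Mullen results: "The mean at 6 months was 89.9 (sd=18.1) and mean at 24 months 75.7 (sd=22.1"). It then says: "The estimated standard deviation of the change is 4 points (assuming a correlation of 0.60 between the two time points"). The same SD is used again in the next sentence: "with a standard deviation of 4 points, there is a great deal of potential for an intervention to achieve an effect size of 0.889".

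The plan converts that effect size into points ("This effect size would be approximately 3.5 points on the Mullen Scale") and divides by the 14.2-point mean decline to get "or about 25% of the natural decline, which seems reasonable for a drug intervention". The paragraph closes: "Thus, our pilot data once again provide reasonable evidence that our intervention effects are achievable".

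The formal cognitive power statement comes under the next heading and does not use the Mullen SD. It is based on "using a t-test on the final Bayley-III Cognitive Scores shows that when the sample size is 24 participants per arm", with 85% power for an effect size of 0.885. Its effect size has a separate source: "The plausibility of achieving this effect size was assessed using published data from the Bayley III manual".

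**The concern.** The SD of a change score is fixed by the two SDs and their correlation, and the plan gives all three. The stated 4 points is far too small for SDs near 20 and a correlation of 0.60, and it equals the plain difference between the two SDs. Every later step about the cognitive effect in that paragraph inherits it.

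In the readable text, this paragraph is the only numerical argument from TSC patients for the size of the cognitive effect. The other TSC support, in the Background and earlier under Primary Study Objective, is qualitative, and the Bayley-III manual comparison concerns a different diagnostic group. A funder, a DSMB member or someone planning the Phase III trial would take from it that the study is powered to detect a one-quarter reduction in cognitive decline. They could then read a null cognitive result as evidence against a benefit of that size.

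**Working it through.** **Inputs** (all from the Mullen paragraph unless noted)
- 6 months: mean 89.9, SD 18.1. 24 months: mean 75.7, SD 22.1.
- Mean decline: 89.9 − 75.7 = 14.2.
- Correlation 0.60; stated SD of change 4; effect size 0.889.
- Formal power statement, next heading: 24 per arm, effect size 0.885, two-sided alpha 0.05, 85% power.

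**The plan's own chain.** 0.889 × 4 = 3.56, reported as about 3.5; 3.5 / 14.2 = 24.6%, reported as about 25%. The multiplication and division are right; the 4 is not.

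**SD of change on the stated inputs**

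SD = √(s₁² + s₂² − 2·r·s₁·s₂) = √(327.61 + 488.41 − 480.01) = √336.01 = 18.33.

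With these SDs the smallest possible value is 22.1 − 18.1 = 4.0, reached only at r = 1.00.

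**Effect in Mullen points**
- SD of change, r = 0.60: 0.889 × 18.33 = 16.3 points; 16.3 / 14.2 = 115% of the decline.
- 24-month SD, the match for a t-test on final scores: 0.885 × 22.1 = 19.6 points; 138%.
- 24-month SD adjusted for baseline, r = 0.60: 22.1 × √(1 − 0.36) = 17.68; 0.885 × 17.68 = 15.6 points; 110%.

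**Sensitivity to r** (effect size 0.889 on the SD of change)

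| r | SD of change | Points | Share of 14.2 |
|---|---|---|---|
| 0.10 | 27.13 | 24.1 | 170% |
| 0.50 | 20.40 | 18.1 | 128% |
| 0.60 | 18.33 | 16.3 | 115% |
| 0.70 | 16.00 | 14.2 | 100% |
| 0.80 | 13.27 | 11.8 | 83% |
| 0.90 | 9.80 | 8.7 | 61% |
| 0.99 | 4.90 | 4.4 | 31% |
| 1.00 | 4.00 | 3.6 | 25% |

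The plan itself varies the within-person Bayley correlation from 0.10 to 0.80; the rows above 0.80 only show how extreme r must be to approach 25%.

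**Could the 4 be something else?** As a standard error of the mean change it would need 18.33 / √n = 4, so n = 21. The number of paired scores is not given, so this is an assumption. A standard error cannot convert a standardized effect into points in any case. The square root of the difference in variances is 12.7, and the baseline-adjusted SD is 17.7. Neither is near 4.

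**Power** (two-sided two-sample t-test, 24 per arm, alpha 0.05, noncentral t)
- d = 0.885: 85.1%, which reproduces the plan's 85%. d = 0.889: 85.4%.
- A true 3.5-point difference: d = 3.5 / 18.33 = 0.191, power 9.9%; d = 3.5 / 22.1 = 0.158, power 8.4%; d = 3.5 / 17.68 = 0.198, power 10.3%.
- Preventing the entire 14.2-point decline: d = 14.2 / 22.1 = 0.64, power 59%; d = 14.2 / 18.33 = 0.77, power 75%.

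**The case against.** The best defence does not dispute the arithmetic; it disputes the weight.

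- **The Mullen text does not set the sample size.** The plan derives N from available resources, the seizure comparison and Bayley-III power, and takes the effect size from the Bayley-III manual. This stands, and it is why the point concerns a rationale and not the design.
- **The pilot decline may understate the decline in Arm A.** It appears to come from the whole pilot cohort, in which 15 of 40 were still seizure free, whereas Arm A randomizes children with epileptiform EEGs. Suppose, purely as an assumption, that the seizure-free children did not decline at all. The decline in the rest would then be 14.2 × 40/25 = 22.7 points (or 14.2 × 39/24 = 23.1 without the dropout), and 16.3 to 19.6 points would be about 71% to 86% of it. The caveat is fair, but even this favourable case is roughly three times the plan's 25%. The benchmark of 14.2 is also the plan's own.
- **At the top of the plan's correlation range the share falls below 100%.** True: it is 83% at r = 0.80. That still does not support 25%.
- **The figures in this section are not readable here and could hold more TSC data.** They could, so the statement that this is the only quantitative TSC support is limited to the readable text. The arithmetic does not depend on it.
- **The plan never claims power for 3.5 points.** Not in those words, but it equates its target effect size with 3.5 points, so the 8% to 10% figure is informative. It is optional in the fix.

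**Conclusion.** The concern holds. On the plan's own inputs the SD of change is 18.3, not 4, so the 3.5 points and the 25% are wrong by a factor of about 4.6 (18.33 / 4). The assumed cognitive effect is about 16 to 20 Mullen points, roughly the whole mean pilot decline or more, and the paragraph cannot support the claim that the cognitive effect is achievable.

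This rests on the printed SDs and means, on r = 0.60 as the plan assumes, and on the plan's use of the mean pilot decline as denominator. An observed paired SD would change the exact figures, but the plan's 25% requires a correlation of 1.00.

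Not affected: 85% power for 0.885 at 24 per arm, the test, alpha, the Bayley-III manual argument, and the separate pilot argument for the seizure effect. It should be fixed because a stated justification for the primary cognitive effect is wrong as written; it does not call for a redesign.

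**What to change.** Revise the Mullen paragraph under Primary Study Objective:

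1. Replace the SD of 4 in both places with 18.3, labelled as the value implied by SDs of 18.1 and 22.1 at r = 0.60. If the sponsor holds the paired pilot scores, give the observed SD of change and its n instead.
2. Delete the 3.5 points, the 25% and the remark that this is reasonable for a drug intervention.
3. Restate the effect as about 16 to 20 Mullen points, roughly the whole mean pilot decline or more. Say which SD each figure uses, show the range over r, and note that the decline in the randomized population may differ from that in the pilot cohort.
4. Limit the closing sentence so that it no longer covers the cognitive effect. It may stand for the seizure effect.
5. State that the plausibility of the cognitive effect size rests quantitatively on the Bayley-III manual comparison, with qualitative TSC support elsewhere. Use one effect size throughout: it is 0.889 in this paragraph and 0.885 under the next heading.
6. Optionally, note that 24 per arm gives about 8% to 10% power for a 3.5-point Mullen difference.

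The cost is one paragraph of text and, if the observed SD is reported, one descriptive calculation on data the sponsor already holds. Sample size, test, alpha and data collection stay as they are. The stated case for the cognitive effect becomes less favourable.
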